### **5.3. Lifestyle Considerations**

Based on the preliminary results from food-effect cohort in Study INCB 54828-101, no significant food effect was observed. Pemigatinib may be administered with or without food.

Participants should refrain from consumption of red wine, Seville oranges, grapefruit or grapefruit juice, pomelos, exotic citrus fruits, grapefruit hybrids, or fruit juices for 7 days before the start of study treatment until after the final dose, as this can affect the metabolism of the study drug.

### **5.4. Screen Failures**

Screen failures are defined as participants who consent to participate in the clinical study but are not subsequently entered in the study. Individuals who do not meet the criteria for participation in this study (screen failure) may be rescreened no more than 1 time.

Tests with results that fail eligibility requirements may be repeated once during screening if the investigator believes the result to be in error. Additionally, a participant who fails screening may repeat the screening process 1 time if the investigator believes that there has been a change in eligibility status. Participants who rescreen must reconsent and be assigned a new participant number.

## 5.5. Replacement of Participants

No participants will be replaced at any time during this study.

# 6. STUDY TREATMENT

## 6.1. Study Treatment Administered

Table 11 and Appendix B present the study treatment information. The starting dose of pemigatinib for all participants is 13.5 mg QD.

**Table 11: Study Treatment Information**

	Study Treatment 1	Study Treatment 2 (Phosphate binder, only for Japan)	
Study treatment name:	Pemigatinib	Bixalomer	Lanthanum carbonate hydrate
Dosage formulation:	Tablet	Capsule	Tablet
Unit dose strength(s) /dosage level(s):	13.5 mg, 9 mg, and 4.5 mg	250 mg	250 mg
Route of administration:	Oral	Oral	Oral
Administration instructions:	One tablet taken every morning (unless otherwise directed)	The usual starting dose of bixalomer for adults is 500 mg 3 times daily just before meals. The dose can be adjusted based on symptoms and serum phosphate concentration. The maximum daily dose should not exceed 7500 mg.	The usual starting dose of lanthanum carbonate hydrate for adults is 750 mg 3 times daily immediately after meals. The dose can be adjusted based on symptoms and serum phosphate concentration. The maximum daily dose should not exceed 2250 mg.
Packaging and labeling:	Pemigatinib will be provided in bottles; each bottle will be labeled as required per country requirement.	Bixalomer will be labeled as required per country requirement.	Lanthanum carbonate hydrate will be labeled as required per country requirement.
Storage:	Room temperature (15°C-30°C)	1°C-30°C	1°C-30°C

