### 6.5.2. Management of Hyperphosphatemia

Hyperphosphatemia is an expected on-target pharmacologic effect of FGFR inhibition. Hyperphosphatemia should be managed with diet modifications, phosphate binders and diuretics, or a dose reduction per the recommendations in [Table 13](#).

The use of diet modifications alone include food exchanges from high-phosphate foods to low-phosphate foods and can be implemented once serum phosphate levels are above the ULN but do not exceed 7.0 mg/dL. Diet modification should continue with the inclusion of phosphate binders once serum phosphate levels exceed 7.0 mg/dL. Examples of phosphate binders are sevelamer HCl (examples of brand names: Renegel® or Renvela®) or lanthanum HCl.

Administration of phosphate binders should be 3 times per day (eg, with each meal) to reduce absorption of phosphate. Doses and frequency of doses should be based on the participant's tolerance for the binder and the control of serum phosphate. If binders are used to manage hyperphosphatemia during treatment, it is recommended to stop binders at the same time pemigatinib is stopped to reduce the risk of hypophosphatemia.

For grading of hyperphosphatemia, please note that CTCAE v5.0 now has a category for hyperphosphatemia.

For Japanese participants, the phosphate binders bixalomer or lanthanum carbonate hydrate will be provided by the sponsor for the treatment of hyperphosphatemia, when required (see [Table 13](#)).

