**Table 13: Recommended Approach for Hyperphosphatemia Management**

Serum Phosphate Level	Supportive Care	Guidance for Interruption/Discontinuation of Pemigatinib	Guidance for Restarting Pemigatinib
> 5.5 mg/dL and ≤ 7 mg/dL	Initiate a low-phosphate diet.	No action.	Not applicable.
> 7 mg/dL and ≤ 10 mg/dL	Initiate/continue a low-phosphate diet and initiate phosphate-binding therapy. Monitor serum phosphate approximately twice a week and adjust the dose of binders as needed; continue to monitor serum phosphate at least twice a week until level returns to ≤ 7 mg/dL.	If serum phosphate level continues to be > 7 mg/dL and ≤ 10 mg/dL with concomitant phosphate-binding therapy for 2 weeks, or if there is recurrence of serum phosphate level in this range, interrupt pemigatinib for up to 2 weeks.	Restart at the same dose when serum phosphate is < 7 mg/dL. If serum phosphate level recurs at > 7 mg/dL, restart pemigatinib with dose reduction.
> 10 mg/dL	Continue to maintain a low-phosphate diet, adjust phosphate-binding therapy, and start/continue phosphaturic agent. Continue to monitor serum phosphate approximately twice a week until level returns to ≤ 7 mg/dL.	If serum phosphate level is > 10 mg/dL for 1 week following phosphate-binding therapy and low-phosphate diet, interrupt pemigatinib. If there is recurrence of serum phosphate level in this range following 2 dose reductions, permanently discontinue pemigatinib.	Restart pemigatinib at reduced dose with phosphate binders when serum phosphate is < 7 mg/dL.

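### Table 11 sets the usual starting dose of lanthanum at its stated daily maximum, which leaves no room to increase from that start under the adjustment text of Tables 11 and 13

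*Protocol*

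**What the plan says.** Protocol Table 11 (Section 6.1) lists two phosphate binders as a second study treatment, for Japan only. For lanthanum carbonate hydrate, in 250 mg tablets, the administration cell makes three statements in sequence:

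- Starting dose: "The usual starting dose of lanthanum carbonate hydrate for adults is 750 mg 3 times daily immediately after meals".
- Adjustment: "The dose can be adjusted based on symptoms and serum phosphate concentration".
- Cap: "The maximum daily dose should not exceed 2250 mg".

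The bixalomer cell has the same structure. It opens with "The usual starting dose of bixalomer for adults is 500 mg 3 times daily just before meals", repeats the adjustment sentence, and gives a daily maximum of 7500 mg.

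Table 13 (Section 6.5.2) says how binders are to be used. For serum phosphate above 7 and up to 10 mg/dL, sites start a binder and then: "Monitor serum phosphate approximately twice a week and adjust the dose of binders as needed". Monitoring continues until phosphate is back to 7 mg/dL or below. Above 10 mg/dL the instruction is to "adjust phosphate-binding therapy, and start/continue phosphaturic agent". The text of Section 6.5.2 adds: "Doses and frequency of doses should be based on the participant's tolerance for the binder and the control of serum phosphate".

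Section 6.2 says that the sponsor supplies both binders in Japan, under the same accountability rules as study drug, and refers to a Japan-specific Pharmacy Manual for further guidance. Appendix F shows that the binder information was added in Amendment 3, so it is current text.

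**The concern.** A starting dose followed by an adjustment sentence and then a maximum normally describes a range within which the dose can move. For lanthanum the start and the maximum are the same amount. A site that starts at the usual dose and finds phosphate still above 7 mg/dL is told to adjust the binder, but cannot raise lanthanum without exceeding the cap in the same table cell.

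There are two possibilities. One of the figures may not be what the sponsor intended, in which case participants would be started at, or capped at, an unintended dose of a sponsor-supplied treatment. Or the start at the ceiling may be deliberate, in which case the table does not say so and the adjustment sentence can mislead sites. Either possibility justifies a check, because these are operative dosing instructions.

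**Working it through.** The maximum is a stated figure and is not derived from anything else in the documents, so there is no plan calculation to reproduce. The check compares the starting daily dose with the stated cap.

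**Inputs, all from Table 11**

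| | Lanthanum carbonate hydrate | Bixalomer |
|---|---|---|
| Usual starting dose per intake | 750 mg | 500 mg |
| Intakes per day | 3 | 3 |
| Stated maximum per day | 2250 mg | 7500 mg |
| Unit strength | 250 mg | 250 mg |

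**Formulas**

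- Starting dose per day = dose per intake × intakes per day.
- Headroom = stated maximum − starting dose per day.
- Range = stated maximum ÷ starting dose per day.

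**Lanthanum**

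- Start: 750 × 3 = 2250 mg/day.
- Headroom: 2250 − 2250 = 0 mg.
- Range: 2250 ÷ 2250 = 1.0.
- In tablets: 2250 ÷ 250 = 9 per day at the start and 9 per day at the maximum.

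**Bixalomer**

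- Start: 500 × 3 = 1500 mg/day.
- Headroom: 7500 − 1500 = 6000 mg.
- Range: 7500 ÷ 1500 = 5.0.

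**Against the adjustment text.** The same adjustment sentence appears in both cells. For bixalomer it permits movement in both directions from the usual start. For lanthanum it permits movement only downward. Table 13 applies its adjustment instruction while phosphate is above 7 mg/dL, and again above 10 mg/dL, so the direction that it most naturally implies is the one closed off for lanthanum. Nowhere else does the protocol give a different lanthanum start or maximum, or say that the drug is started at its ceiling on purpose. The SAP gives no binder doses.

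**The case against.** The strongest case on the other side is that nothing here is a strict contradiction. A dose equal to the maximum does not exceed it, so both sentences can be obeyed at once. Neither table uses a word for increase. Adjustment for symptoms or tolerance can mean lowering the dose, and Section 6.5.2 ties dosing to tolerance as well as to phosphate control. The starting dose is described as usual, not mandatory, and 250 mg tablets allow a lower start with room to rise. Sites also have a second supplied binder, diet and, above 10 mg/dL, a phosphaturic agent. Table 13 is headed as a recommended approach. Bixalomer is a different drug, so its five-fold range sets no standard for lanthanum. The Japan-specific Pharmacy Manual, which is not available here, may explain the figures.

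All of this stands, and it limits the point to a missing range that needs an explanation. It does not remove the point: from the usual start there is no increase to make, while the instruction to adjust applies exactly when phosphate is too high.

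Three stronger readings are tempting, and the documents do not support them:

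- A reader might infer that the tables require upward adjustment and so cannot be followed. They say only that the dose is adjusted.
- A reader might infer that starting at the ceiling leads to more pemigatinib interruptions or reductions under Table 13. A participant at the maximum already receives the most lanthanum that the protocol allows. Nothing shows that control fails more often than if the dose had been raised to the same cap in steps.
- A reader might guess that one figure is a transcription slip, for example a daily amount entered as an amount per intake. Nothing in Table 11 or Section 6.5.2 points to that.

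**Conclusion.** The point holds as a query about consistency. The usual lanthanum start in Table 11 takes up 2250 of the 2250 mg allowed per day, which leaves 0 mg for an increase. This does not fit comfortably with the adjustment sentence in the same cell or with Table 13.

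The arithmetic needs no assumption. The one judgement is that adjusting a binder while phosphate is above 7 mg/dL most naturally means increasing it. The documents do not show which figure, if any, is wrong, and a start at the maximum may be intended. The scope is Japanese participants given lanthanum. No effect on the response-rate endpoints or their analysis has been shown. The passages should nevertheless be reconciled, because the figures are live dosing instructions for a treatment that the sponsor supplies.

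**What to change.** The sponsor should check the lanthanum starting dose and maximum daily dose in Table 11 against the source from which they were taken. The two figures should then be reconciled with each other, with the adjustment sentence in Table 11 and with the binder-adjustment instructions in Table 13. If starting at the maximum is intended, Table 11 should say so, and the adjustment text should make clear what adjustment means for a participant already at the cap. The Japan-specific Pharmacy Manual should be checked for agreement with whatever is decided. This review does not propose a dose.

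The cost is a correction or a clarifying sentence in Table 11, matching wording in Table 13 if needed, and a notice to Japanese sites. No change to the design, sample size or analysis is involved.

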## 6.2. Preparation, Handling, and Accountability

The investigator, investigational drug storage manager (for Japan), or designee must confirm appropriate temperature conditions have been maintained during transit for all study treatments received and any discrepancies are reported and resolved before use of the study treatment.

Only participants enrolled in the study may receive study treatment, and only authorized site staff may supply or administer study treatment. All study treatment must be stored in a secure, environmentally controlled, and monitored (manual or automated) area in accordance with the labeled storage conditions with access limited to the investigator, investigational drug storage manager (for Japan), and authorized site staff.

The investigator, investigational drug storage manager (for Japan), or designee is responsible for study treatment accountability, reconciliation, and record maintenance (ie, receipt, reconciliation, and final disposition records). Inventory and accountability records must be maintained and readily available for inspection by the study monitor and are open to inspection at any time by any applicable regulatory authorities. The investigator, investigational drug storage manager (for Japan), or designee must maintain records that document:

- Delivery of study drug to the study site.
- Inventory of study drug at the site.
- Participant use of the study drug including pill counts from each supply dispensed.
- Return of study drug(s) to the investigator, investigational drug storage manager (for Japan), or designee by participants.

The investigational product must be used only in accordance with the Protocol. Tablets are not to be crushed, dissolved or broken. The investigator (or investigational drug storage manager for Japan) will also maintain records adequately documenting that the participants were provided the specified study drug. These records should include dates, quantities, and any available batch or serial numbers or unique code numbers assigned to the investigational product and study participants.

Completed accountability records will be archived by the site. The investigator, investigational drug storage manager (for Japan), or designee will be expected to collect and retain all used, unused, and partially used containers of study drug until verified by the study monitor (unless otherwise agreed to by the sponsor). At the conclusion of the study, the investigator, investigational drug storage manager (for Japan), or designee will oversee shipment of any remaining study drug back to the sponsor or its designee for destruction according to institutional SOPs. If local procedures mandate on-site destruction of investigational supply, the site should (where local procedures allow) maintain the investigational supply until the study monitor inspects the accountability records in order to evaluate compliance and accuracy of accountability by the investigative site. At sites where the study drug is destroyed before monitor inspection, the monitors rely on documentation of destruction per the site SOP.

Further guidance and information for the final disposition of unused study treatments are provided in the Pharmacy Manual.

For Japan, the phosphate binders bixalomer and lanthanum carbonate hydrate will be provided by the sponsor (see [Table 11](#)). The requirement for the accountability, reconciliation, and record

maintenance of the binders is the same as for study drug as described above. Further guidance and information is provided in the Japan-specific Pharmacy Manual.

### **6.3. Measures to Minimize Bias: Randomization and Blinding**

This is an open-label, nonrandomized study. There is no randomization and no blinding.

### **6.4. Study Treatment Compliance**

Compliance with all study-related treatments and assessments should be emphasized to the participant by the site personnel, and appropriate steps should be taken to optimize compliance during the study.

Compliance with pemigatinib will be calculated by the sponsor based on the drug accountability documented by the site staff and monitored by the sponsor/designee (tablet counts). Participants will be instructed to bring all study drugs with them to the study visits in order for site personnel to conduct tablet counts to assess study drug accountability. The drug accountability documentation will be used by the sponsor to calculate treatment compliance.

### **6.5. Dose Modifications**

Individual decision regarding dose modifications of pemigatinib should be made using clinical judgment and in consultation with the sponsor's medical monitor, taking into account relatedness of the AE to the study treatment and the participant's underlying condition. Adverse events that have a clear alternative explanation or transient ( $\leq 72$  hours) abnormal laboratory values without associated clinically significant signs or symptoms, may be exempt from dose-reduction rules.

#### **6.5.1. Criteria and Procedures for Dose Interruptions and Adjustments of Study Drug**

Safety concerns should be discussed with the sponsor immediately upon occurrence or awareness to determine if the participant should continue or discontinue study treatment.

Treatment with pemigatinib may be delayed up to 2 weeks (14 days) to allow for resolution of toxicity. Participants may resume treatment if no medical condition or other circumstance exists that, in the opinion of the investigator, would make the participant unsuitable for further participation in the study. The treating investigator should contact the sponsor to discuss the case of any participant whose treatment has been delayed for more than 14 days before restarting treatment with pemigatinib. See [Table 12](#) for guidelines.

**Table 12: Guidelines for Interruption and Restarting of Study Drug**

Adverse Event	Action Taken
Chemistry	

 
AST and/or ALT is <math>> 5.0 \times</math> ULN.
 
 
Note: In participants with liver metastasis-related elevations at baseline, contact sponsor to discuss clinical management and possible dose reductions.
	
Step 1: Interrupt pemigatinib up to 2 weeks (14 days) until the toxicity has resolved to <math>\leq</math> Grade 1 except by approval of the medical monitor.
 
Step 2: Restart pemigatinib at same dose. If assessed as related to pemigatinib, restart pemigatinib at next lower dose; monitor as clinically indicated.

Other toxicities	

 
Any Grade 1 or Grade 2 toxicity.
 
	
Continue pemigatinib treatment and treat the toxicity; monitor as clinically indicated.

 
Any Grade 3 toxicity, if clinically significant and not manageable by supportive care.
 
	
Step 1: Interrupt pemigatinib up to 2 weeks (14 days), until toxicity resolves to <math>\leq</math> Grade 1.
 
Step 2: Restart pemigatinib at same dose. If assessed as related to pemigatinib, restart pemigatinib at next lower dose; monitor as clinically indicated.

 
Any recurrent Grade 3 toxicity after 2 dose reductions.
 
	
Discontinue pemigatinib administration and follow-up per Protocol. (Exceptions require approval of sponsor.)

 
Any other Grade 4 toxicity.
 
QT/QTc to <math>> 500</math> milliseconds or to <math>> 60</math> milliseconds over baseline.
 
	
Discontinue pemigatinib administration and follow-up per Protocol.

The sponsor recommends a maximum of 2 dose level reductions: participants administered 13.5 mg can decrease to 9 mg, and if additional dose reduction is required, participants can decrease to 4.5 mg. Dose reductions below 4.5 mg are not allowed. The frequency of dosing remains the same (QD) as well as the schedule (continuous dosing). After a dose reduction, a dose re-escalation is not permitted.

For participants who are up-titrated from 13.5 mg to 18 mg, study drug can be decreased to 13.5 mg, and if additional dose reductions are required, participants can decrease to 9 mg and then to 4.5 mg. Dose reductions below 4.5 mg are not allowed.

For participants who present with possible or confirmed SRD/RPED based on optical coherence tomography, the guidelines in [Table 12](#) should be followed. It is recommended to discuss the findings with the Incyte medical monitor before making changes to the participant's treatment.

Per CTCAE v5.0, retinal detachment is graded as 3 (macular sparing) and 4 (macula-off), but this refers to rhegmatogenous retinal detachment (when a hole occurs in the retina). There is no grading for SRD/RPED (no hole in the macula, just fluid accumulation). Therefore, grading should be based on the CTCAE v5.0 term of retinopathy.

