### 6.5.4. Criteria for Permanent Discontinuation of Study Drug

The occurrence of unacceptable toxicity not caused by the underlying disease will require that the study drug be permanently discontinued. Unacceptable toxicity is defined as follows:

- Occurrence of an AE that is related to study drug that, in the judgment of the investigator or the sponsor's medical monitor, compromises the participant's ability to continue study-specific procedures or is considered to not be in the participant's best interest.
- An AE requiring more than 2 dose reductions.
- Persistent AE requiring a delay of therapy for more than 2 weeks (14 days) unless a greater delay has been approved by the sponsor.
- Increase in QT/QTc to  $> 500$  milliseconds or to  $> 60$  milliseconds over baseline. In case of a QTc  $> 500$  milliseconds, the participant must be hospitalized and continuous ECG monitoring must be set up until the measure of the QTc interval decreases below 500 milliseconds and is acceptable in the opinion of the local cardiologist.

See Section 7 for discontinuation procedures.

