### **8.3.6. Laboratory Assessments**

See [Table 15](#) for the list of clinical laboratory tests to be performed, and see the SoA ([Table 4](#)) for the timing and frequency. A central laboratory will analyze all [REDACTED] translational samples. The site's own local laboratories will perform all clinical laboratory assessments for safety (ie, blood chemistries, hematology assessments, coagulation tests, endocrine function and urinalysis).

Serum phosphate testing is required on Day 8 in Cycles 2+ if a participant develops hyperphosphatemia during Cycle 1 or in later cycles if the participant is up-titrated. Parathyroid hormone (endocrine) testing is required at baseline and Day 1 of every third cycle (starting with Cycle 3) as parathyroid hormone plays a role in calcium and phosphate hemostasis ([Khundmiri et al 2016](#)).

Additional testing may be required by the sponsor based on emerging safety data. All Protocol-required laboratory assessments must be conducted in accordance with the Laboratory Manual and the SoA (see [Table 4](#)). Information regarding collection, processing, and shipping of laboratory assessments is provided in the Laboratory Manual.

Clinically significant abnormal laboratory findings are those that are not associated with the underlying disease, unless judged by the investigator to be more severe than expected for the participant's condition. All laboratory tests with values considered clinically significantly abnormal during participation in the study or within 30 to 35 days after the last dose of study treatment should be repeated until the values return to normal or baseline or are no longer considered clinically significant by the investigator or medical monitor.

Screening laboratory assessments for hematology, chemistry, and coagulation must be performed within 14 days of Cycle 1 Day 1. If performed more than 14 days before Cycle 1 Day 1, then the tests must be repeated; if performed within 3 days of C1D1, additional laboratory sample testing is not required (see [Table 4](#)). Laboratory samples collected on study Day 1 must be performed

before study treatment administration. After Cycle 1, predose laboratory procedures can be conducted up to 72 hours before study treatment administration (within the 3-day study window), and results should be reviewed by the investigator or qualified designee and found to be acceptable before a new cycle of treatment is initiated.

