8.3.3. Potential Hy's Law Events

The participants with elevated ALT or AST $> 3 \times$ upper limit of normal range and alkaline phosphatase $< 2 \times$ upper limit of normal range accompanied by total bilirubin $> 2 \times$ upper limit of normal range at the same visit will be listed by cohort.

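### No protocol rule is keyed to the SAP's potential Hy's Law combination, and Table 12 guides a restart after a related Grade 4 AST/ALT rise that recovers within 14 days

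*Protocol*

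**What the plan says.** Protocol 6.5.1, Table 12, has one liver row, under its Chemistry heading. The trigger is AST and/or ALT above 5.0×ULN, with no upper limit. Step 1 interrupts drug for up to 14 days until the event is back to Grade 1 or less, unless the medical monitor approves otherwise. Step 2 restarts at the same dose, with this variant: "If assessed as related to pemigatinib, restart pemigatinib at next lower dose; monitor as clinically indicated". A note covers one special group: "In participants with liver metastasis-related elevations at baseline, contact sponsor to discuss clinical management and possible dose reductions".

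Bilirubin has no row, so it falls under Other toxicities:
- Grade 1 or 2: "Continue pemigatinib treatment and treat the toxicity; monitor as clinically indicated".
- Grade 3: interrupt only if judged clinically important and beyond supportive care.
- "Any other Grade 4 toxicity": discontinue.

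Protocol 6.5.4 adds permanent stops. One is for a delay beyond 14 days, unless the sponsor has approved longer. Another is "An AE requiring more than 2 dose reductions". A third is by judgment, for a related event where continuing "is considered to not be in the participant's best interest".

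SAP 8.3.3 defines the potential Hy's Law combination: ALT or AST >3×ULN and alkaline phosphatase <2×ULN, with total bilirubin >2× "upper limit of normal range at the same visit will be listed by cohort". Its only output is Listing 2.8.8. The protocol text does not mention the combination.

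**The concern.** The sponsor has picked out a liver pattern worth reporting but gives the investigator no instruction for it. In part of its range the literal Table 12 instruction is to keep dosing. Separately, a related Grade 4 rise in AST or ALT is guided towards restart, while other Grade 4 toxicities are guided towards a stop, and the protocol gives no reason for the difference.

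What is at stake is participant safety and consistency between sites. Whether drug is held in the gap depends on each investigator and medical monitor, not on a stated limit. No effect on ORR, power or alpha is claimed.

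**Working it through.** The plan states no figure to reproduce. The check applies the Table 12 rows to the SAP combination and then counts what the restart rule permits.

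**Step 1. The rows applied to the SAP combination** (alkaline phosphatase <2×ULN throughout)

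| ALT/AST | Total bilirubin | Objective Table 12 action |
|---|---|---|
| >3 to 5×ULN | >2×ULN, Grade 1–2 | None; the row says continue |
| >3 to 5×ULN | Grade 3 | None; a hold rests on two judgments |
| >3 to 5×ULN | Grade 4 | Discontinue |
| >5×ULN | >2×ULN, below Grade 4 | Interrupt; restart when AST/ALT recovers |
| >5×ULN | Grade 4 | Discontinue |

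The documents do not print the CTCAE bilirubin cut-offs. They were varied as assumptions: Grade 3 above 2.5, 3 or 4×ULN, paired with Grade 4 above 8, 10 or 12×ULN. The cut-offs move participants between the first two rows but never create an objective hold there, because the result follows from the row wording.

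In the >3 to 5×ULN band the AST/ALT row is not reached, so no interruption begins on that row and its 14-day clock never starts. Above 5×ULN the recovery condition refers to the AST/ALT event alone. Bilirubin could still be raised when that row permits restart.

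**Step 2. Related Grade 4 AST/ALT**

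The Chemistry row has no ceiling, so Grade 4 values fall inside it. The stop row sits under a different heading and is limited by the word *other*. On the plain reading it does not cover AST/ALT. If a site reads it as covering them, the same event falls under two rows with opposite actions, so the wording needs repair either way.

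**Step 3. Redosings the rule permits**

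Assume each event is related, recovers to Grade 1 or less within 14 days, and nobody intervenes.

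- From 13.5 mg: event 1, restart at 9 mg; event 2, restart at 4.5 mg; event 3 would need a third reduction and a dose below 4.5 mg, so stop. Redosings = 2.
- From 18 mg under 6.5.4: 13.5 mg, 9 mg, stop. Redosings = 2.
- From 18 mg under the 6.5.1 dose ladder: 13.5 mg, 9 mg, 4.5 mg, stop. Redosings = 3.

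These counts describe the rule. They are not a risk estimate.

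**Step 4. Who could meet the limits at entry (Table 10)**

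- Liver metastases: ALT/AST is excluded only above 5×ULN, bilirubin at 2.5×ULN or more, and alkaline phosphatase at 3×ULN or more. A participant with ALT >3 to 5, bilirubin >2 to <2.5 and alkaline phosphatase <2×ULN can enter already meeting all three limits.
- Gilbert's syndrome without liver metastases: bilirubin >2 to <2.5×ULN is allowed, with ALT/AST below 3×ULN. If alkaline phosphatase is below 2×ULN, a later ALT or AST rise alone completes the combination.

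Any new rule therefore needs a baseline adjustment for both groups.

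**Step 5. Frequency**

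Table 7 (events in at least 10%) and Table 8 (serious events in at least 1%) name no transaminase or bilirubin term. Nor do the most frequent related serious events in Protocol 2.3, which are named down to 2/665 = 0.30%. This suggests rarity, but it measures neither event.

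**The case against.** The strongest reply is that the protocol already provides for these events. Table 12 is headed as guidance. Section 6.5 puts dose decisions to clinical judgment with the medical monitor. Section 6.5.1 sends safety concerns to the sponsor at once, to settle whether treatment continues, and lets drug resume only if the investigator finds the participant suitable. Section 7.1.1 stops injurious participation. Section 8.3.6 says predose "results should be reviewed by the investigator or qualified designee and found to be acceptable before a new cycle of treatment is initiated". There is 24-hour SAE reporting and an internal monitoring committee. Special warnings sit in the Investigator's Brochure, which is not available here. The SAP listing is a reporting device and contradicts nothing in the protocol. Participants must have no other therapy likely to help, so rechallenge at a lower dose can be reasonable.

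Much of this stands, and it rules out stronger readings that a reader might infer:

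- *Nothing objective acts on the combination while bilirubin is below Grade 4.* Not so. Above 5×ULN the AST/ALT row requires interruption whatever the bilirubin.
- *Redosing after Grade 4 AST/ALT is automatic.* Not so. It needs recovery to Grade 1 or less (or monitor approval), sponsor discussion and investigator agreement.
- *Apart from Grade 4 bilirubin, every safeguard is judgment.* Not so. The 14-day delay stop in 6.5.4 is objective unless the sponsor extends it, and the dose-reduction limit is a fixed count.

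What the reply does not supply is a limit for the combination. None of these provisions names it, and the predose review gives no liver threshold for an acceptable result. The protocol does use numbers for other hazards: QTc above 500 ms, or more than 60 ms over baseline, forces a stop, and phosphate above 10 mg/dL has hold and stop rules. A numeric liver rule would match that practice.

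**Conclusion.** The point holds in a limited form and is worth a cheap amendment.

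- The combination: no protocol rule is keyed to it. The gap without an objective hold is ALT/AST >3 to 5×ULN with bilirubin above 2×ULN but below Grade 4. Above 5×ULN the gap is narrower: drug is held, but the AST/ALT row sets no bilirubin condition for restart.
- Related Grade 4 AST/ALT: if it recovers to Grade 1 or less within 14 days, the guidance is restart one level lower, with at most 2 redosings from 13.5 mg, and 2 or 3 from 18 mg depending on which section governs. This rests on the plain reading of *other* in the Grade 4 row.

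The case for a hold on the combination is the firmer of the two. A permanent stop after a recovered Grade 4 rise is more debatable in participants without alternatives, so the remedy should keep a route to rechallenge. The documents give no event rate. Both events are likely rare, and the documents do not support a claim that participants have been harmed or that the efficacy analysis is affected.

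**What to change.** **1. Table 12 and 6.5.4, new entry.** Suggested wording:

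> ALT or AST >3×ULN with total bilirubin >2×ULN and alkaline phosphatase <2×ULN at the same postbaseline visit: interrupt at once, notify the medical monitor and repeat the tests; discontinue permanently unless another cause is documented. The 6.5 exemption for transient laboratory values does not apply to the hold.

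For any participant with raised baseline values (liver metastases or Gilbert's syndrome, both allowed by Table 10), require worsening from baseline by a multiple that the sponsor's safety group sets.

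**2. Table 12, AST/ALT row.** State the Grade 4 action outright:

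> Grade 4 AST or ALT assessed as related to pemigatinib: discontinue; rechallenge only with documented approval of the sponsor's medical monitor.

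**Optional, SAP 8.3.3.** Restrict the listing to postbaseline events and flag participants who met the limits at baseline.

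**Cost.** Two short protocol additions at the next amendment and, if wanted, one SAP sentence. All four analytes are already in the Table 15 chemistry panel, which Table 4 schedules on Cycle 1 Days 1, 8 and 15 and Day 1 of each later cycle, so no new scheduled visits are needed; the only added tests are the repeats after a trigger. The downside is occasional extra holds, and a few participants with no other therapy may lose rechallenge.
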